Anal continence. OH and LH are both excisional operations. Anal continence has been a concern after these operations. Anal incontinence is defined as involuntary loss of air, liquid or solid stool that is a social or hygienic problem¹⁸. The anal cushions contribute to the closure of the anal canal and provide 15- 20% of maximal resting pressure of the anal canal¹⁹. A Cochrane review found that anal incontinence was reported in 1.6% of the patients after conventional hemorrhoidectomy²⁰. Another Cochrane review reported 3,6 % anal continence or hygiene problems at 1-2 years follow-up after conventional hemorrhoidectomy¹². When patients are actually asked for symptoms of incontinence a retrospective multicenter study found that 33% of the patients reported anal incontinence after hemorrhoidectomy and 10% meant this was caused by the operation²¹. Another study found some deterioration of anal incontinence after hemorrhoidectomy in patients with preoperative impaired continence²². Anal continence after LigaSure™ hemorrhoidectomy is scarcely investigated.

Previous studies comparing Open Hemorrhoidectomy and LigaSure™ Hemorrhoidectomy

Open Hemorrhoidectomy and LigaSure™ are both techniques where the hemorrhoids are excised, (ablative techniques). A few studies indicates that ablative techniques have better long term results in terms of reduction of symptoms^{11,23}.

There are so far 18 controlled studies comparing OH to LH²⁴⁻⁴¹, all designed for and using postoperative pain as major outcome variable. There are three metanalysis the largest including 11 studies^{42,43,44}. In conclusion there seems to be less post procedural pain, somewhat faster recovery, slightly less bleeding and shorter operating time after LH.

Patient' satisfaction was evaluated in a few studies with no difference between the two operations^{29,40,41}. One small study on 30 patients investigated anal continence with no difference between the two operations³⁰.

No study has investigated hemorrhoidal symptoms with a validated instrument one year or more after the operation

Rationale

Hemorrhoidal Disease is a benign disease and should be evaluated by its effect on hemorrhoidal symptoms together with its effect on quality of life.

Hemorrhoidal symptoms should be the main outcome variable when evaluating surgery for hemorrhoidal disease. This information is largely lacking.

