We will also analyze: anal function with anal manometry, anatomical result as evaluated by the surgeon, operation time, theatre time (time consumed in the operating room), postoperative complications, postoperative pain and need of analgesics, length of postoperative hospital stay and days before return to work or possibility of return to work.

SUBJECT CRITERIA

Subject Inclusion Criteria

In order to be eligible to participate in this study, an individual must meet all of the following criteria:

- Male or female aged 18 to 85 at the time of randomization
- Grade III-IV hemorrhoids and grade II hemorrhoids refractory to previous treatment with rubber band ligation or sclerotherapy.
- Hemorrhoidal symptom score of four or more
- Colonoscopy, sigmoidoscopy or rigid rectoscopy within 3 months before inclusion.
- American Society of Anesthesiologists (ASA) score of I or II. (day-care surgery)
- Provide signed and informed consent form

Subject Exclusion Criteria

An individual who meets any of the following criteria will be excluded from participation in this study:

- Previous operation of grade III and IV hemorrhoids within the last 2 years.
- Previous operation for anal incontinence.
- Active anal fistula or anal fissure
- Incontinence for solid stool

- Active immunosuppressive therapy (increased risk of anorectal sepsis)
- Cirrhosis / portal hypertension
- Mb Crohn⁴⁷

DESIGN AND METHOD

Trial Design

This is a single center randomized clinical trial comparing two operative techniques in the treatment of hemorrhoids.

Qualification of the surgeons

The surgeon should have experience from at least ten open hemorrhoidectomies and ten LigaSure™ hemorrhoidectomies before operating independently

Operation date and type of anesthesia

Operation time, theater time, operative bleeding, grading of complexity of the operation and type of anesthesia is recorded by the surgeon after the operation in “Protokol for operation” (appendix 8)

Study Interventions – Open Hemorrhoidectomy (OH)

Patient Material and Recruitment

According to the power calculation at least 62 subjects are needed for the analysis.

Compensating for an estimated loss to follow-up of approximately 10%, 70 subjects will be included in the study. See statistical considerations in a later chapter.

Subjects for this study will be recruited consecutively from patients attending the proctologic outpatient clinic at the department of surgery at Holbæk Hospital eligible for operation.

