The procedure is repeated for each hemorrhoid taking care of leaving adequate "skin bridges" between each excision.

Postoperative Care

All patients will be discharged on the day of the operation unless there are any immediate postoperative complications or if the patient is living alone without attendance at home the first 24 postoperative hours.

Standard postoperative pain treatment is initiated for all patients regardless of operation type and consists of:

Paracetamol tablet 1-gram x4/day for 7 days, hereafter p.n.

Ibuprofen tablet 400mg x3/day for the first 7 days, hereafter p.n. (patients \geq 65 years old will receive supplementary Pantoprazole tablet 40mgx1/day when using ibuprofen)

Morphine tablet 10mg p.n. Max 6 tablets/day for 3 days

Magnesia tablet 1gx2/day for 7 days, hereafter p.n.

Xylocaine gel p.n.

At discharge from the hospital and in the preoperative material (appendix 1) patients are informed that there are no limitations concerning physical activity and they are encouraged to return to daily activity as soon they feel fit enough and the postoperative pain permits it. Patients are told not to drive, operate heavy machinery or performing other potentially dangerous tasks while on morphine.

Postoperative pain and return to daily activities

During the first 14 postoperative days the patient will report postoperative pain, use of analgesics and return to daily activities or work in "Patientdagbog" (appendix 10). Since weekends and holidays can influence when a patient returns to work, patients will answer a question when they feel fit enough to return to work. *It will also be noted if the patient is self-employed.*

Immediate postoperative course

Immediate postoperative complications, postoperative pain, use of analgesics and length of hospital stay will be noted in "Sygehusprotokol" (appendix 9).

Evaluation of symptoms

The questionnaire "Protokol for symptomer" (appendix 3) is used for evaluating hemorrhoidal symptoms recorded by the subject. Five questions on pain, itching, bleeding, soiling and prolapse graded from 0-4. Resulting in a score of 0-20.

The hemorrhoidal symptoms will be evaluated preoperatively at randomization, after 3 months, one-, three- and five years.

Patient's satisfaction with the operation will be evaluated on a 7-grade Lichert scale.

Evaluation quality of life

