
The primary outcome variable is symptom score based on the patient questionnaire. The five questions graded from 0 to 4 results in a score from 0 to 20. Preliminary data from an ongoing study in our center comparing OH with THD and using the same questionnaire shows a symptom score after 3 months of 5 with a standard deviation (SD) of 4,2. The power calculator on www.stat.ubc.ca comparing the means for two independent samples with a two sided test has been used. We postulate that a difference of 3 points in symptom score would be clinically relevant with the standard deviation of 4,2. To demonstrate a difference in mean score of 3 points with a SD of 3.5 in both groups, an alpha error of 5% and a beta error of 20%, 31 patients in each group is needed.

As for the secondary objectives analyzing anal incontinence by the Wexner score and the Revised Fecal Incontinence Scale, both consists of five questions graded from 0 to 4 results in a score from 0 to 20. Preliminary data from the study mentioned above shows a mean of 4 and SD of 3,9 for the Wexner score and a mean of 2,3 with an SD of 3,9 for the RFIS. To demonstrate a difference in mean score of 3 points with a SD of 3.9 in both groups, an alpha error of 5% and a beta error of 20%, 27 patients in each group is needed.

Patient satisfaction is analyzed after year on a scale from 1 to 7. Preliminary data from the above-mentioned study shows a mean of 5,8 and a SD of 1,6. Assuming that a difference in 1,5 points would be clinically relevant 19 patients are needed in each group with an alpha error of 5% and a beta error of 20%.

Thus a sample size of 31 patients in each group should provide sufficient power in addressing analysis of primary and secondary endpoints. We estimate that there will be a loss of 9 patients for follow up. We will include 70 patients in the study.

ETHICS

The investigators will ensure that this study is conducted in full conformity with the principles set forth in the Declaration of Helsinki seventh edition⁵¹.

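### Days to return to work may be right-censored at day 14: the recording described is a 14-day diary, with no later capture and no rule for patients not yet back

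*Combined protocol and SAP*

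**What the plan says.** After the three numbered secondary outcomes, the section on secondary outcome variables lists further analyses, the last of which is "days before return to work or possibility of return to work". The variable is a duration in days.

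The section on postoperative pain and return to daily activities describes how it is recorded: "During the first 14 postoperative days the patient will report postoperative pain, use of analgesics and return to daily activities or work", in the patient diary (appendix 10). Because weekends and holidays can affect the actual date, the same paragraph adds that "patients will answer a question when they feel fit enough to return to work". It does not say on which form, or when, that question is put.

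The other recording points are described without return to work. For the hospital form: "Immediate postoperative complications, postoperative pain, use of analgesics and length of hospital stay will be noted". For follow-up: "The hemorrhoidal symptoms will be evaluated preoperatively at randomization, after 3 months, one-, three- and five years". Continence, manometry and anatomy follow the same schedule, and quality of life is recorded at baseline and from one year on.

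The statistical section gives no method for this variable, no expected return time or SD, and no rule for a patient still off work when the diary ends.

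**The concern.** A variable measured in days needs a date for each patient, or an explicit censoring rule. As described, a patient who goes back on day 20 leaves a diary showing no return, and nothing described later supplies the date. The choice of analysis cannot recover a date that was never collected.

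The loss need not be equal between arms. The protocol's summary of earlier comparisons is that after the LigaSure operation "there seems to be less post procedural pain, somewhat faster recovery". If that is true here, more open-hemorrhoidectomy patients will run past day 14, and the unrecorded times will be the ones that separate the arms most. Comparing mean days with those patients left out, or entered as 14, would then understate the advantage the background leads one to expect.

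**Working it through.** **Is there a figure to reproduce?** No. The protocol states no mean, SD, sample size or power for return to work. What can be checked is how far a day-14 limit could distort the comparison, and every return-time input to that check is an assumption.

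**Inputs.** From the protocol: the 14-day window, and the expected direction (somewhat faster after LigaSure hemorrhoidectomy, LH, than after open hemorrhoidectomy, OH). Assumed: log-normal times with median m and log-SD s, for several pairs of medians and s from 0.4 to 0.7.

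**Formulas.** With z = ln(14/m)/s and Φ the standard normal distribution function:

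- true mean = m·exp(s²/2)
- share returning after day 14 = 1 − Φ(z)
- partial mean A = m·exp(s²/2)·Φ(z − s)
- mean with late times set to 14 = A + 14·(1 − Φ(z))
- mean with late returners dropped = A/Φ(z)

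**Worked case: s = 0.5, medians OH 10 and LH 7.** exp(0.125) = 1.133.

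- True means: 11.33 and 7.93, difference 3.40.
- z: ln(1.4)/0.5 = 0.673 and ln(2)/0.5 = 1.386, so 25.0% and 8.3% are late.
- A: 11.33 × 0.569 = 6.44 and 7.93 × 0.812 = 6.44.
- Set to 14: 6.44 + 14 × 0.2505 = 9.95 and 6.44 + 14 × 0.0828 = 7.60, difference 2.35 (69% of the true value).
- Dropped: 6.44/0.7495 = 8.60 and 6.44/0.9172 = 7.02, difference 1.57 (46%, from unrounded values).

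**Range.** The same formulas give the rows below; simulation of 2,000,000 times per arm agreed to within 0.02 days in the rows where it was run (log-SD 0.5 to 0.7).

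| log-SD | Medians OH/LH | Late OH/LH | True difference | Set to 14 | Dropped |
|---|---|---|---|---|---|
| 0.4 | 6/4 | 2%/0.1% | 2.17 | 2.13 (98%) | 2.01 (93%) |
| 0.5 | 7/5 | 8%/2% | 2.27 | 2.00 (88%) | 1.59 (70%) |
| 0.5 | 10/7 | 25%/8% | 3.40 | 2.35 (69%) | 1.57 (46%) |
| 0.6 | 12/8 | 40%/18% | 4.79 | 2.34 (49%) | 1.42 (30%) |
| 0.5 | 14/10 | 50%/25% | 4.53 | 1.94 (43%) | 1.19 (26%) |
| 0.7 | 21/15 | 72%/54% | 7.67 | 1.14 (15%) | 0.75 (10%) |

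The direction is the same in every row. The size depends almost wholly on how many patients return after day 14.

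**Medians.** Setting late times to 14 leaves a group median below 14 where it was. At 12/8 the median difference is 4 days before and after capping, although the mean difference has halved. A median above day 14 cannot be estimated from the diary.

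**Censored analysis.** Power was simulated with 31 per arm (the primary outcome's number), log-SD 0.5 and 1,500 repetitions:

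| Medians OH/LH | Rank test, all dates known | Rank test, late times tied at 14 | Log-rank, censored at 14 |
|---|---|---|---|
| 10/7 | 0.77 | 0.76 | 0.73 |
| 14/10 | 0.73 | 0.69 | 0.65 |
| 21/15 | 0.71 | 0.54 | 0.53 |

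The first two power columns use the same test, so the gap between them is the loss due to the window. It is negligible at 10/7 and 0.17 at 21/15.

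**The case against.** A reader might infer that the 14-day diary is the sole source and that the difference between the operations is therefore shrunk. The documents support neither step.

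On the source, the fit-for-work question has no stated form or date, and the diary and follow-up forms are appendices that are not reproduced in the text available. The diary might ask for an expected date, or a later form might ask about work. What can be said is that no later capture is described. Even so, a question about fitness would not by itself supply the actual date of return.

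On the shrinkage, the protocol names no analysis for this variable. The calculator used for the primary outcome, "comparing the means for two independent samples with a two sided test has been used", says nothing about return to work. Attenuation appears only if late returners are dropped or set to 14 and the result is read as a difference in mean days. A Kaplan-Meier or log-rank analysis censored at day 14, or the proportion back by day 14, compares the arms validly over that period. A mean capped at 14 is also legitimate if it is labelled as a mean restricted to 14 days.

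Nor is the share of late returners known. These are mostly day-case patients with no activity restrictions who are encouraged to resume normal life early, so the near-zero rows of the table cannot be ruled out.

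All of this stands, and it limits the point to a conditional one. It does not remove the point: no rule for late returners is stated, and a valid censored analysis still says nothing about recovery after day 14.

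**Conclusion.** The point holds in a limited form. As described, days to return to work may be right-censored at day 14, and the protocol neither collects the later dates nor says how patients without one are handled. A comparison of mean days with late returners dropped or set to 14 would be biased toward no difference. A censored analysis would be valid but would lose what happens after day 14.

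The size cannot be stated from the documents. Under assumed log-normal times, setting late returns to 14 keeps between 98% and 15% of the true mean difference, and dropping them keeps between 93% and 10%. The low end requires more than half of each arm to return after day 14.

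The importance is low. This is an additional analysis, not the primary or a numbered secondary outcome, and no sample size rests on it. The one-year symptom comparison is unaffected. It is worth correcting because the correction is cheap and the dates become harder to obtain once the 3-month visit has passed.

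**What to change.** - At the scheduled 3-month visit, ask patients whose diary shows no return by day 14 for two dates: actual return to work, and first fit for work.
- State on which form, and when, the existing fit-for-work question is asked.
- Pre-specify both as time-to-event outcomes (Kaplan-Meier curves, log-rank test). Censor a patient without a date at the last contact at which they were known not to have returned, or at day 14 if there was no later contact.

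The cost is one short item at a visit that already takes place, plus a few lines in the statistical section. The drawback is some recall error in dates given by late returners at 3 months. Patients back within 14 days keep their diary dates.

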The use of a validated symptom score with long term follow-up could yield important information for the choice of treatment of hemorrhoidal disease.

Postoperative complications and adverse effects

Serious complications to hemorrhoidal operations occur rarely. The most commonly early complications are urinary retention, bleeding or fever/infection. Late complications are anal fissure, anal stenosis and anal incontinence. A Cochrane review reported after open hemorrhoidectomy; postoperative bleeding 2.9%, urinary retention 5.1%, anal fissure 3.1%, anal stenosis 0,9% and anal incontinence 1.6%²⁰.

Search Methods

A PubMed database search was conducted with following PICO query:

```
((("haemorrhoids"[All Fields] OR "hemorrhoids"[MeSH Terms] OR "hemorrhoids"[All Fields]) AND (((Open[All Fields] AND ("hemorrhoidectomy"[MeSH Terms] OR "hemorrhoidectomy"[All Fields] OR "haemorrhoidectomy"[All Fields])) OR Milligan-Morgan[All Fields]) OR ("diathermy"[MeSH Terms] OR "diathermy"[All Fields]))) AND (Ligasure[All Fields] OR (Ligasure[All Fields] AND ("hemorrhoidectomy"[MeSH Terms] OR "hemorrhoidectomy"[All Fields] OR "haemorrhoidectomy"[All Fields]))) AND ("complications"[Subheading] OR "complications"[All Fields])
```

A Cochrane was done searching for h(a)emorroidectomy and h(a)emorroid.

Relevant articles were chosen and by title and abstract and by reading the reference lists further texts were identified. In addition Danish and Swedish guidelines from national medical journals were included.

OBJECTIVES

Aim

To analyze and compare the long-term effects of LigaSure™ hemorrhoidectomy (LH) and Open Hemorrhoidectomy (OH) on hemorrhoidal symptoms.

Main outcome variable

Symptoms related to hemorrhoids one year postoperatively, according to a validated hemorrhoidal symptom score (HDSS)(appendix 3).

Secondary outcome variable

- 1) Patient satisfaction with the operation one year postoperatively, evaluated on a seven grade Lichert scale.
- 2) Quality of Life as evaluated by Short health Scale (SHS), Short Form 36 (SF36) and EuroQualityofLife -5 Dimensions (EQ-5D-5L) (appendix 6).
- 3) Anal continence as evaluated by the Wexner score⁴⁵, the Revised Fecal Incontinence Scale (RFIS) ⁴⁶.

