Quality of life will be evaluated by SHS, SF-36 and EQ-5D-5L, recorded by the patient preoperatively at the randomization and one, three and five years postoperatively (appendix 7).

Evaluation of anal continence

Anal continence will be evaluated using both the Wexner score and the RFIS, registered by the patient in "protokol for symptomer" (appendix 3). Five questions with a score from 0-4 resulting in a total score of 0-20 for both operations. Evaluation will be done preoperatively at randomization, after 3 months, one-, three- and five years.

Anal function will also be analyzed with anal manometry preoperatively at randomization, after 3 months, one-, three- and five years. In addition we will investigate the amount of smooth muscle in the resected specimen from the two groups indicating the amount of injury to the internal anal sphincter.

Evaluation of hemorrhoidal anatomy

Hemorrhoidal anatomy is evaluated by the surgeon using “Protokol for anatomi”(appendix 7). Late postoperative complications are also reported in “Protokol for anatomi” at follow-up.

Hemorrhoids are graded according to the Goligher classification⁶:

Grade	Grade of prolapse
I	No prolapse, just prominent blood vessels
II	Prolapse upon bearing down or by physical exercise with spontaneous reduction
III	Prolapse upon bearing down and requires manual reduction
IV	Prolapse which cannot be manually reduced

Table 1: Goligher’s classification of internal hemorrhoids

The classification of hemorrhoids is based on physical examination by the surgeon and patient history. If prolapse is not present at physical examination the patient can be classified as having grade II or III based on the patient history. External skin flaps will also be recorded in “Protokol for anatomi” (Appendix 7).

Hemorrhoidal anatomy will be evaluated preoperatively at randomization, operatively and after 3 months, one-, three- and five years.

Security control

In order to detect adverse events and non-satisfactory results a security control of the study will be performed after operation of 10 patients in each arm. An open control of the immediate postoperative course, postoperative complications and postoperative hemorrhoidal symptoms three months after the operation will be performed.

STATISTICAL CONSIDERATIONS

Study Hypothesis

There is no difference in hemorrhoidal symptoms one year after an operation for hemorrhoids performed as LigaSure™ Hemorrhoidectomy or Open Hemorrhoidectomy.

Sample Size Considerations

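### Does a study hypothesis of no difference, beside a test sized to detect 3 points, let a non-significant result pass as proof of similarity?

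*Combined protocol and SAP*

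**What the plan says.** Under Statistical Considerations, Study Hypothesis, the combined protocol and SAP gives one sentence: "There is no difference in hemorrhoidal symptoms one year after an operation for hemorrhoids performed as LigaSure™ Hemorrhoidectomy or Open Hemorrhoidectomy". No alternative hypothesis is written beside it.

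Sample Size Considerations, directly below, says that a power calculator "comparing the means for two independent samples with a two sided test has been used". It sets the target: "We postulate that a difference of 3 points in symptom score would be clinically relevant with the standard deviation of 4,2". The sizing sentence then begins "To demonstrate a difference in mean score of 3 points with a SD of 3.5 in both groups" and ends "an alpha error of 5% and a beta error of 20%, 31 patients in each group is needed". Patient Material and Recruitment carries this forward: "According to the power calculation at least 62 subjects are needed for the analysis".

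The Aim, under Objectives, is worded neutrally: "To analyze and compare the long-term effects of LigaSure™ hemorrhoidectomy (LH) and Open Hemorrhoidectomy (OH) on hemorrhoidal symptoms".

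The document states no equivalence or non-inferiority margin, no planned confidence interval and no rule for interpreting a non-significant result. It also does not say that such a result will be read as showing the operations to be the same.

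**The concern.** A test of difference can reject a hypothesis of no difference but cannot establish it. If the Study Hypothesis is what the investigators hope to show, the only test in the plan cannot show it. The 3 points called clinically relevant are used for sizing and for nothing else.

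What is at stake is the conclusion. The Ethics section says there is no evidence that either method is better, so a non-significant result is quite possible. It also says the trial should inform later treatment choices, including their economic side, and the Introduction notes that new devices raise operative costs. A claim of similar symptoms at one year would bear on that choice. If the claim rested on p > 0.05 alone, it might be made while the data were still compatible with a difference that the plan itself calls relevant.

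**Working it through.** **Inputs**, all from Sample Size Considerations: difference 3 points, two-sided alpha 5%, power 80%, 31 per group, and two SDs, 4.2 (preliminary data) and 3.5 (sizing sentence).

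**1. Reproduce the plan's figure.** n per group = 2 × (1.960 + 0.842)² × (SD/3)², normal approximation.
- SD 4.2: 2 × 7.85 × 1.96 = 30.8, so 31. This matches the plan.
- SD 3.5: 2 × 7.85 × 1.361 = 21.4, so 22. This does not match.

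The 31 therefore rests on SD 4.2. That SD describes three-month scores in a study of a different pair of operations, so the one-year SD is unknown and both values are carried below.

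**2. Precision at 31 per group.** SE = SD × √(2/31); half-width of the 95% interval = t(0.975, 60 df) × SE, with t = 2.000.

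| | SD 4.2 | SD 3.5 |
|---|---|---|
| SE | 1.067 | 0.889 |
| Half-width | 2.13 | 1.78 |
| Non-significant, interval still reaches 3 | observed difference 0.87 to 2.13 | observed difference 1.22 to 1.78 |

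The lower limit of each range is 3 minus the half-width. For example, at SD 4.2 an observed 1.5 gives 1.5 ± 2.13, or about -0.6 to 3.6.

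**3. How often this happens if the true difference is 0.**
- SD 4.2: P(|d| < 0.87) = 2Φ(0.866/1.067) - 1 = 0.58, so the interval lies wholly within ±3. P(0.87 < |d| < 2.13) = 0.95 - 0.58 = 0.37, so the result is non-significant with 3 points still open.
- SD 3.5: 2Φ(1.222/0.889) - 1 = 0.83 within ±3, and about 0.12 non-significant with 3 points open.

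Simulation gives the same figures: 0.582 and 0.369 at SD 4.2, 0.828 and 0.123 at SD 3.5.

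**4. If a true difference exists (SD 4.2).**

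| True difference | Trials non-significant | Of those, interval includes 3 points |
|---|---|---|
| 1 | 85% | 51% |
| 2 | 55% | 73% |
| 3 | 21% | 88% |

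In most of these ambiguous trials the printed interval would itself show that 3 points had not been excluded.

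**5. What an equivalence rule would require.** With a margin of 3, a true difference of 0 and 80% power, n per group = 2 × (SD × (z + 1.282)/3)².
- SD 4.2: 34 per group with a 90% interval (z = 1.645), 42 with a 95% interval (z = 1.960).
- SD 3.5: 24 and 29.

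So 31 per group would be too few at SD 4.2 and enough at SD 3.5.

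**6. Is 3 points a suitable margin?** Sample Size Considerations gives a preliminary mean of 5, and 3/5 = 60% of it. Under a rule that accepts any interval within ±3, an observed 0.8 at SD 4.2 gives 0.8 ± 2.13, about -1.3 to 2.9. That would be declared free of any relevant difference.

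**The case for a change.** The strongest case for a change is that the plan states only one hypothesis, gives no alternative, and has no primary-analysis section that would settle how the sentence is meant. If it is the null, a few words would say so. If it is the expected conclusion, a criterion fixed before the data are seen is needed. A rule based on the plan's own 3 points would cost nothing in patients or data, and in the 37% of trials found in step 3 it would oblige the authors to call the result inconclusive.

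Part of this stands. Labelling the sentence as the null and writing the two-sided alternative beside it would be tidier, and non-significance alone is not evidence of similarity. But these are matters of wording and reporting. They alter no patient, test or estimate.

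The formal ±3 rule is a different matter. The plan says "We postulate that a difference of 3 points in symptom score would be clinically relevant"; it does not say that anything smaller is unimportant. A difference worth detecting is not automatically a margin within which two operations may be called equal. The rule would authorise an equivalence claim in a trial that was not designed to make one. A single advertised chance of success, such as 58%, would also conceal that the figure moves to 83% under the other SD in the same paragraph.

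**Conclusion.** No change to the plan follows. The hypothesis sentence stands immediately above a two-sided calculation meant to detect a difference, under an aim that only compares. Read as the null, it agrees with the sizing, and no rule in the plan yields a wrong result. The missing guidance on a non-significant outcome is a gap that analysts fill sensibly by reporting the LH-OH difference with its 95% interval beside the 3 points.

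The scope for over-reading is real but uncertain in size. With 31 per group and no true difference, about 37% of trials at SD 4.2 and about 12% at SD 3.5 would be non-significant with 3 points still open. The chance of an interval wholly within ±3 is about 58% and 83% respectively. These figures assume equal SDs, approximately normal mean differences and 62 analysable patients. If all 70 were analysed at SD 4.2, the 37% would fall to about 27%.

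The one substantive alternative, adopting 3 points as an equivalence margin, is a trade-off with no clear gain, because the plan offers no justification for that margin. The conclusion would differ if the investigators intended a formal equivalence claim, which would need its own justified margin and sample size. Nothing in the document indicates that they do.
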